4. I have read and understand the information in the Investigators' Brochure (or Manufacturer's Brochure) regarding the risks and potential benefits. I agree to conduct the protocol in accordance with Good Clinical Practices (ICH-GCP), the applicable ethical principles, the Statement of Investigator (Form FDA 1572), and with local regulatory requirements. In accordance with the FDA Modernization Act, I will ensure the registration of the trial on the www.clinicaltrials.gov website.
5. I agree to maintain adequate and accurate records in accordance with IRB policies, Federal, state and local laws and regulations.

UCSF Principal Investigator / Study Chair

Printed Name

Signature

Date

Principal Investigator

Site

Printed Name

Signature

Date

Participating Site(s)

Mount Sinai Comprehensive Cancer Center [name] [REDACTED]
	
Angeles Clinic [name] [REDACTED]
	
California Pacific Medical Center, [name] [REDACTED]

Stanford University Cancer Institute [name] [REDACTED] [REDACTED]
	
Comprehensive Cancer Centers of Nevada [name] [REDACTED] [REDACTED]
	
Cincinnati Oncology, [name] [REDACTED] [REDACTED]

MD Anderson, [name] [REDACTED] [REDACTED]
	
Dana Farber [name] [REDACTED] [REDACTED]
	
University of Pennsylvania, [name] [REDACTED] [REDACTED]

H Lee Moffitt Cancer Center [name] and [name] [REDACTED] [REDACTED] [REDACTED]
		

Abstract

Title	Phase II trial of targeted kinase fusion inhibition in unresectable stage III/IV BRAF/NRAS wild-type melanoma
Patient population	Patients with metastatic melanoma who are wild-type (WT) status for BRAF, NRAS, and who also have an oncogenic kinase fusion.
Rationale for Study	BRAF WT melanoma patients currently have no options for molecularly targeted therapy. Given the low response rate to currently approved immunotherapies, there is a need for more therapeutic options in patients with BRAF/NRAS WT metastatic melanoma.
Primary Objective	
 To estimate the clinical activity of tyrosine kinase inhibitors matched to the activated kinase fusion partner in patients with metastatic melanoma.
Secondary Objectives	
 To estimate tumor stability in kinase fusion melanoma patients treated with kinase inhibitors matched to the activated fusion partner. To estimate survival in kinase fusion melanoma patients treated with kinase inhibitors matched to the activated fusion partner. To examine the safety and tolerability of kinase inhibitors in patients with the kinase fusion targets.
Exploratory Objectives	
 To explore molecular mechanisms of resistance for patients who progress on therapy.
Primary Endpoint	
 Confirmed ORR by RECIST v1.1 at 24 weeks.
Secondary Endpoints	
 Confirmed CBR (defined as CR or PR or SD for >24 weeks). Determination of PFS and OS. Evaluation of the adverse effect profile, using CTCAE v4.03, of each kinase inhibitor.
Exploratory Endpoints	
 Exploratory endpoints to include assessment of expression levels of the fusion kinase protein, reported as percentage by IHC staining. Measures taken at baseline and after 4 weeks of therapy will be summarized. Changes in expression level will be assessed between baskets using a paired t-test if data permit. For patients who progress on therapy, an additional biopsy may be obtained and will be compared with baseline expression levels if data permit.
Study Design	This is a phase II multi-center prospective basket trial designed to test the hypothesis that targeting specific kinase fusions in metastatic melanoma with pre-specified kinase inhibitors will result in objective tumor shrinkage and durable response. The study design is a 2 stage optimal design with a sample size of N=35, with n1=11 during stage I and n2=24 during stage II. If 1 or fewer responses are observed during stage I, the trial will be stopped. If 6 or fewer responses are observed by the end of stage II, the trial will be stopped.

Number of patients	Estimating a drop-out rate of 20%, we anticipate enrolling 44 patients to accrue 35 evaluable patients.
Study Drugs	Capmatinib, Entrectinib, Ceritinib, Regorafenib
Safety Assessments	Physical exam with evaluation of vital signs, performance status, and toxicity grading as per CTCAE v4.03. Clinical laboratory evaluations including CBC, CMP.
Efficacy Assessments	ORR and CBR to be assessed as per RECIST v1.1 criteria.

List of Abbreviations

AE	adverse event
ALT	alanine aminotransferase
AST	aspartate aminotransferase
AUC	area under the curve
CBC	complete blood cell (count)
CBR	clinical benefit rate
CR	complete response
CRC	Clinical Research Coordinator
CRC	Colorectal Cancer
CRF	case report form
CT	computerized tomography
CTCAE	Common Terminology Criteria for Adverse Events
CTMS	Clinical Trial Management System
DLT	dose limiting toxicity
DSMC	Data and Safety Monitoring Committee
DSMP	Data and Safety Monitoring Plan
ECG	electrocardiogram
ECOG	Eastern Cooperative Oncology Group
FDA	Food and Drug Administration
FIH	First in Humans
GCP	Good Clinical Practice
GI	gastrointestinal
HBcAb	Hepatitis B core antibody
HBeAg	Hepatitis B “e” antigen
HBsAb	Hepatitis B surface antibody
HBsAg	Hepatitis B surface antigen
HDFCCC	Helen Diller Family Comprehensive Cancer Center
HFSR	hand foot skin reaction
HIV	human immunodeficiency virus
ICH	International Conference on Harmonization
IC50	concentration resulting in 50% inhibition
IHC	immunohistochemistry
IND	investigational new drug application
INR	international normalized ratio
IP	investigational product

List of Abbreviations

IRB	Institutional Review Board
IV	intravenous
LDH	lactate dehydrogenase
LLN	lower limit of normal
MRI	magnetic resonance imaging
NCI	National Cancer Institute
NSCLC	non-small cell lung cancer
ONJ	osteonecrosis of the jaw
ORR	overall response rate
OS	overall survival
PD	disease progression
PFS	progression free survival
PK	pharmacokinetics
PO	Per os (by mouth, orally)
PR	partial response
PRC	Protocol Review Committee (UCSF)
PT	prothrombin time
PTT	partial thromboplastin time
RBC	red blood cell (count)
SD	stable disease
SD	standard deviation
SGOT	serum glutamic oxaloacetic transaminase
SGPT	serum glutamic pyruvic transaminase
TSH	thyroid stimulating hormone
ULN	upper limit of normal
UPCR	urine protein-to-creatinine ratio

Table of Contents

Protocol Signature Page 2

UCSF Principal Investigator / Study Chair..... 2

Principal Investigator Site 2

Participating Site(s)..... 3

List of Abbreviations 6

List of Abbreviations 7

1.1 Fusion Kinases in Melanoma..... 11

1.2 Kinase Inhibitors..... 11

1.3 Rationale for the Proposed Study..... 12

1.4 Correlative Studies 13

2 Objectives of the Study 13

2.2 Secondary Objectives 13

2.3 Exploratory Objectives, Other Assessments..... 13

3 Endpoints of the Study 13

3.2 Secondary Endpoints 14

3.3 Exploratory Endpoints 14

4 Study Design 14

Table 1. Kinase Fusion and Assigned Drug..... 14

4.2 Number of Subjects 15

4.3 Eligibility Criteria..... 15

Appendix 6 Capmatinib (see attached document)

Appendix 7 Ceritinib (see attached document)

Appendix 8 Regorafenib (see attached document)

Appendix 9 Entrectinib (see attached document)

Table 1. Kinase Fusion and Assigned Drug

Table 2. Drug Regimens

Table 3. Response Criteria

1 Introduction

Melanoma

Melanoma is the deadliest of all skin cancers, with an incidence rate that is rising worldwide. It is estimated that in 2013, in the US alone, over 80,000 cases of melanoma were diagnosed and over 8,000 patients died of this disease¹. Fortunately, recent advances in immunotherapy have led to the development of several new agents for metastatic melanoma: the FDA-approved ipilimumab and pembrolizumab, as well as promising PD-L1 antibodies. Another major advancement in melanoma therapy has been in the field of molecularly targeted therapy: BRAF inhibitors with/without MEK inhibitors were recently shown to have benefit in patients whose tumors harbor BRAF mutations²⁻⁴.

While 40-50% of cutaneous melanomas have activating BRAF mutations⁵, there remains a sizable BRAF wild type (WT) subset of melanoma that still lacks effective molecularly-targeted therapy options⁶. While 30-40% of patients respond to currently approved immunotherapies, many patients with BRAF WT metastatic melanoma are in need of more treatment options^{7,8}. The major subsets among BRAF WT are currently recognized as those with a mutation of NRAS^{9,10} as a molecular driver (15-20% across all primary sites except ocular) and those which test WT for both BRAF and NRAS⁶.

1.1 Fusion Kinases in Melanoma

Targeting fusion Kinases

There is emerging data that a subset of cutaneous melanomas without mutations in BRAF, NRAS, KIT, GNAQ¹¹ or GNA11¹² feature activating kinase fusions. We recently discovered in melanocytic neoplasms including melanomas without these mutations the presence of fusions involving the kinases ROS1 (17%), NTRK1 (16%), ALK (10%), BRAF (5%), RET (3%) and MET^{13,14}. The kinase fusions occurred in a mutually exclusive pattern and invariably fused the kinase domains of the respective genes to a variety of N-terminal fusion partners. We showed that the chimeric fusion kinases are enzymatically active and act as constitutively activated drivers of multiple oncogenic signaling pathways. Importantly, cognate kinase inhibitors can inhibit these pathways.

Determination of Specific Kinase Fusions

Identification of kinase fusions can be performed by various methods and is offered by different CLIA laboratories. A separate study protocol aimed at determining the frequency of kinase fusions in BRAF WT melanoma will provide testing through a UCSF CLIA laboratory and report potentially actionable results to the patient's clinician. In this study protocol, fusion kinase detection will be performed using a validated targeted next-

generation sequencing platform. Additional methods that may be employed include fluorescence in situ hybridization and immunohistochemistry. We expect most eligible patients for this study to be tested by the UCSF CLIA laboratory, however, we will accept confirmation of a kinase fusion after review of the test results from other CLIA approved laboratories (i.e. Foundation Medicine)..

1.2 Kinase Inhibitors

Capmatinib (INC280)

INC280 is an ATP-competitive, reversible inhibitor of the c-MET receptor tyrosine kinase. INC280 is highly selective for c-MET (IC₅₀ value of 0.13 nM) as compared to a panel of 56 other human kinases tested. In pre-clinical models, INC280 was shown to have activity against a c-MET amplified gastric cancer cell line (GTL-16) and a c-MET amplified HCC cell line (HCCLM3). Over three phase I trials, 161 patients have been treated with various doses of INC280 with 2.2-8.1% of patients experiencing dose-limiting toxicities. The most common adverse effects were diarrhea, nausea, and vomiting. INC280 is still being evaluated in multiple Phase I and II studies.

Ceritinib

Ceritinib is an ATP-competitive, piperidine tyrosine kinase inhibitor with 20 times the potency against ALK compared to crizotinib (IC₅₀ value of 0.15 nM compared to 3 nM). Ceritinib also has inhibitory activity against INSR and IGF1R, though 50-fold less potency than for ALK (IC₅₀ values of 7 nM and 8 nM, respectively²¹). In pre-clinical models, ceritinib was shown to have activity against crizotinib-resistant ALK-positive NSCLC. In a phase I clinical trial, 59 patients with ALK-rearranged malignancies were enrolled²². The maximum tolerated dose was 750 mg once daily. Dose limiting toxicities included diarrhea, vomiting, elevated AST/ALT, and hypophosphatemia. Among 140 patients, the overall response rate was 58%. In eighty patients who had progressed on crizotinib, ORR was 56%. Amongst patients who received at least 400 mg of ceritinib per day, the median progression free survival was 7 months and the median duration of response was 8.2 months. Additionally, ceritinib was shown to have activity against CNS lesions in patients who had progressed on prior therapy with crizotinib.

Ceritinib was granted accelerated approval by the FDA in April 2014 for the treatment of ALK-positive, metastatic NSCLC with disease progression on or who are intolerant of crizotinib. The phase I study (CLDK378X2101) is ongoing; enrollment has been completed in the expansion phase with interim data presented at ASCO 2014. Based on a clinical trial of 163 patients with metastatic ALK-positive NSCLC, treatment with ceritinib resulted in an ORR of 54.6% with a median duration of response of 7.4 months. The complete response (CR) rate was 1.2% and the partial response (PR) rate was 53.4%²³.

Regorafenib

Regorafenib is a carboxamide BRAF and CRAF kinase inhibitor initially developed to target VEGF driven xenografts. This compound also inhibits multiple transmembrane and intracellular kinases RET, VEGFR1, VEGFR2, VEGFR3, KIT, PDGFR-alpha, PDGFR-beta, FGFR1, FGFR2, TIE2, DDR2, Eph2A, CRAF, BRAF, BRAF^{V600E}, SAPK2, PTK5, and Abl²⁴. Regorafenib was recently approved for use in metastatic CRC based

on a placebo controlled Phase III clinical trial²⁵. The median overall survival was prolonged from 5 months in the placebo group to 6.4 months in the regorafenib group. The median PFS was similar and response rates were similar. The safety profile of regorafenib is typical of the VEGF inhibitors and includes asthenia/fatigue, decreased appetite and food intake, hand-foot skin reaction, diarrhea, mucositis, weight loss, infection, hypertension and dysphonia. Regorafenib has also been shown to provide significant improvement in PFS compared with placebo in patients with metastatic gastrointestinal stromal tumor (GIST), and is now an approved treatment for GIST^{26,27}. We have additional data that BRAF fusion melanoma cell lines are more sensitive to regorafenib and sorafenib, both class II BRAF inhibitors, than to vemurafenib, a class I BRAF inhibitor (¹⁴ and unpublished data, [name]).

Entrectinib (RXDX-101)

Entrectinib is a potent inhibitor of the tyrosine kinases encoded by genes NTRK1, NTRK2, NTRK3, ROS1 and ALK, with IC50 values for kinase inhibition ≤ 12 nM. In pre-clinical models, entrectinib has demonstrated concentration-dependent inhibition of Trk, ROS1, and ALK phosphorylation in cell-based assays using tumor cell lines. It has also demonstrated dose-related antitumor effects in a variety of human tumor xenograft and allograft models dependent on Trk, ROS1, or ALK oncoproteins: namely, anaplastic large cell lymphoma, and intracranial non-small cell lung cancer (NSCLC). Importantly, entrectinib has also exhibited potent antitumor activity both in vitro and in vivo against ALK mutants known to be resistant to the ALK inhibitor crizotinib, thus suggesting that entrectinib has the potential to treat patients with brain metastases and those who have crizotinib-refractory disease. Entrectinib was evaluated in two Phase 1 clinical studies (Study ALKA-372-001 and Study RXDX-101-01 [STARTRK-1]) designed to determine the maximum tolerated dose (MTD) and/or recommended Phase 2 dose (RP2D) of entrectinib in patients with advanced or metastatic solid tumors harboring NTRK1/2/3, ROS1, or ALK molecular alterations. Doses tested ranged from 100 to 1200 mg/m², under fasted and fed conditions in both intermittent and continuous daily dosing regimens. Two DLTs were observed: one event of Grade 3 cognitive impairment and one event of Grade 3 fatigue. Both events were reversible upon study drug interruption. Based upon these two DLTs, 400 mg/m² administered once-daily on a fed regimen was selected as the BSA-based RP2D. Subsequently, additional expansion cohorts of patients were enrolled to further explore a fixed daily dosing regimen, and 600 mg/day was selected as the RP2D.

1.3 Rationale for the Proposed Study

Current effective treatments for melanoma include immunotherapy and targeted molecular therapies. However, not all patients respond to immunotherapy, and currently approved targeted molecular therapy is indicated only for patients with activating BRAF mutations. Recently, fusion kinases have been identified in melanoma that are mutually exclusive with activating mutations in BRAF. In other cancers, inhibition of similar fusion kinases with kinase inhibitors have demonstrated clinical efficacy. We propose a study of a specific kinase inhibitor for patients with metastatic kinase fusion melanoma. Given that patients with kinase fusion melanomas are a rare cohort without extensive FDA-approved treatment options, they stand to derive great benefit from promising novel agents in melanoma. Patients eligible for this study will be those with melanomas that are BRAF/NRAS wild-type and that have an oncogenic kinase fusion, and who have received at least one FDA-approved line of therapy for unresectable/metastatic

melanoma. Patients who are treatment-naïve but who refuse available standard options and prefer to enroll on study as their first line of treatment after a thorough informed consent process will be eligible for this study at the discretion of the treating physician.

1.4 Correlative Studies

The presence of one of the following integral biomarkers will need to be established by tumor biopsy to establish trial eligibility: oncogenic kinase fusion involving ALK, BRAF, MET, NTRK, RET, or ROS1. Patients will be consented for two biopsies: one biopsy after cycle 1, and one biopsy at the time of progression (if applicable).

Punch or core biopsy is mandatory for easily accessible sites (i.e., palpable, cutaneous, or subcutaneous lymph nodes or lesions). All other lesion biopsies (i.e., lung, liver) that pose more than minimal risk are optional and will be determined by the treating Investigator. Correlative studies to be performed on tumor biopsy specimens will include immunohistochemical assessment of fusion kinase expression levels and activation status.

2 Objectives of the Study

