3.3 Exploratory Endpoints

- Exploratory endpoints to include assessment of expression levels of the fusion kinase protein, before and during treatment, reported as percentage by immunohistochemistry (IHC) staining.

4 Study Design

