4.1 Characteristics

This is a phase II prospective multi-center basket trial designed to test the hypothesis that targeting specific kinase fusions in metastatic melanoma with kinase inhibitors matched to the activated kinase fusion will result in tumor response. The study design is a 2-stage optimal design. Patients with a eligible kinase fusion in their melanoma, as identified by a CLIA-approved laboratory (targeted next-generation sequencing of tumor tissue, fluorescence in situ hybridization and immunohistochemistry) will be offered enrollment in this protocol and will be treated in one of five baskets. As testing for fusion kinases is not currently part of the standard of care for melanoma, a separate protocol will provide screening for kinase fusions for patients with BRAF wild-type melanoma in a CLIA-approved laboratory at UCSF. Based on the kinase fusions identified, patients will be stratified as follows:

Table 1. Kinase Fusion and Assigned Drug

MET fusion	Capmatinib 400 mg PO BID
ALK fusion	Ceritinib 450 mg PO q day (with low-fat meal)
RET fusion	Regorafenib 160 mg PO q day (first 21 days of each 28 day cycle)
BRAF fusion	Regorafenib 160 mg PO q day (first 21 days of each 28 day cycle)
NTRK1 fusion NTRK2 fusion NTRK 3 fusion	Entrectinib 600 mg PO q day
ROS1 fusion	Entrectinib 600 mg PO q day

The dose of capmatinib at 400 mg PO BID is based on the recommended phase II dose (RP2D) by Novartis. Ceritinib at 450 mg PO daily with a low-fat meal (approximately 100-500 calories, 1.5-15 grams of fat) demonstrated comparable AUC_{0-24h} and C_{max} at Cycle 2 Day 1 to patients treated with ceritinib 750 mg under fasting conditions (the FDA-approved dose for ALK-rearranged NSCLC resistant to intolerant to crizotinib). Both ceritinib dosing regimens showed similar rates of AEs but GI related AEs and dose interruptions were fewer with dosing at 450mg PO daily with a low-fat meal, and for this reason is the chosen dosing. For regorafenib we will dose at 160 mg PO daily (first 21 days of each 28 day cycle) which is the FDA-approved dose for both colon cancer and GIST. The dose of entrectinib at 600 mg PO QD is the RP2D based on two Phase 1 studies conducted by Ignyta. Please refer to Table 1 for drug assignments and Table 2 for drug dose regimens.

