4.3.1 Inclusion Criteria

Patients eligible for this study will be those with melanomas that are BRAF/NRAS wild-type and that have an oncogenic kinase fusion. Patients who have received at least one

FDA-approved line of therapy for unresectable/metastatic melanoma are eligible. Patients who are treatment-naïve but who refuse available standard options and prefer to enroll on study as their first line of treatment after a thorough informed consent process will be eligible for this study at the discretion of the treating physician.

Further inclusion criteria vary depending on the basket to which the patient will be assigned. Please refer to the drug-specific appendices for further details on inclusion criteria.

- For patients with MET fusion to be treated with capmatinib, see Appendix 6, Section 6.1.
- For patients with ALK fusion to be treated with ceritinib, see Appendix 7, Section 7.1.
- For patients with RET or BRAF fusion to be treated with regorafenib, see Appendix 8, Section 8.1.
- For patients with NTRK1, NTRK2, NTRK3, or ROS1 fusion to be treated with entrectinib, see Appendix 9, Section 9.1.

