5.3 Packaging and Labeling of Study Drugs

Drugs will be packaged and labeled per UCSF institutional standards, adhering to applicable local and federal laws.

6 Treatment Plan

Patients will be treated with an appropriate kinase inhibitor as outlined in Table 1. Cycle length is defined for this study as 4 weeks. Patients will be restaged every 2 cycles (8 weeks), and best objective response will be confirmed using RECIST v1.1 with measurements at a minimum of 4 weeks after the response-defining determination. Dose reductions and dose interruptions for management of toxicity will be specified in the sections below.

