6.1 Dosage and Administration

Treatment will be administered on an outpatient basis. See Table 2 for dosage and administration information.

Table 2. Drug Regimens

Study Drug	Precautions	Start Dose	Dose Level -1	Dose Level -2	Dose Level -3	Route	Schedule	Cycle Length
Capmatinib	Do not take with food (do not eat at least 1 hour before or 2 hours after drug ingestion)	400 mg	300 mg	200 mg	N/A	PO	BID	28 days
Ceritinib	Take with low-fat meal	450 mg	300 mg	150 mg	N/A	PO	Once daily	28 days
Regorafenib	Take each morning with a low-fat breakfast	160 mg	120 mg	80 mg	N/A	PO	Once daily (21 days on, 7 days off)	28 days
Entrectinib	Take within 1 hour following a meal	600 mg	400 mg	200 mg	N/A	PO	daily	28 days

7 Study Procedures and Observations

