7.1 Schedule of Procedures and Observations

The study-specific assessments are detailed in this section. Screening assessments must be performed within 30 days prior to the first dose of investigational product except for the staging which can be done 90 days prior. Any laboratory results falling outside of the reference ranges may be repeated at the discretion of the investigator. All on-study visit procedures are allowed a **window of ± 7 days** unless otherwise noted. Treatment or visit delays for public holidays or weather conditions do not constitute a protocol violation. Additional follow-up visits may be added and additional tests ordered per discretion of treating Investigator.

A written, signed, informed consent form (ICF) and a Health Insurance Portability and Accountability Act (HIPAA) authorization must be obtained before any study-specific assessments are initiated. A copy of the signed ICF will be given to the subject and a copy will be filed in the medical record. The original will be kept on file with the study records.

All patients who are consented will be registered in OnCore[®], the UCSF Helen Diller Family Comprehensive Cancer Center (HDFCCC) Clinical Trial Management System (CTMS). The system is password protected and meets HIPAA requirements.

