Exploratory endpoints will include expression levels (reported as percentage by IHC) of the fusion kinase protein. Measures taken at baseline as well as after four weeks of therapy will be summarized. Changes in expression level will be assessed between baskets using a paired t-test if data permit. For patients who progress on therapy, an additional biopsy may be obtained and will be compared with baseline expression levels if data permit. This will inform on molecular mechanisms of resistance for patients who progress while on therapy.

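### The on-treatment biopsy is not tied to dosing, and for the regorafenib (RET and BRAF) baskets its nominal time falls at the end of the off-week

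*Combined protocol and SAP*

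**What the plan says.** Three places describe the on-treatment sample.

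- Section 1.4 (Correlative Studies) has patients consent to "one biopsy after cycle 1, and one biopsy at the time of progression (if applicable". The tissue is used for immunohistochemical expression of the fusion kinase and also for its activation status.
- Section 3.3 defines the exploratory endpoint as "assessment of expression levels of the fusion kinase protein, before and during treatment".
- Section 9, in its exploratory paragraph, states: "Measures taken at baseline as well as after four weeks of therapy will be summarized". It then plans to assess changes in expression between baskets, provided there are enough data.

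The dosing calendar comes from elsewhere. Section 6 says "Cycle length is defined for this study as 4 weeks", for every drug. Table 1 in Section 4.1 gives "Regorafenib 160 mg PO q day (first 21 days of each 28 day cycle" for RET and BRAF fusions, and Table 2 in Section 6.1 agrees: "Once daily (21 days on, 7 days off". Neither table shows a scheduled break for capmatinib, ceritinib or entrectinib. Section 7.1 allows on-study procedures a "window of ± 7 days" unless noted otherwise.

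Nothing in the text available ties the biopsy to a dosing day, gives regorafenib patients a different time, or asks for the time of the last dose to be recorded with the sample.

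**The concern.** One time point serves four drugs, but one of the four has a week without drug at the end of each cycle. A sample taken at the end of cycle 1 in a RET or BRAF patient follows that week, whereas the same sample in any other basket is taken under continuous scheduled dosing. Basket and recent drug exposure then vary together, and a difference in change from baseline could reflect the dosing calendar and not the drug.

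Activation status is the more exposed readout. In the entrectinib background, Section 1.2 itself reports concentration-dependent inhibition of kinase phosphorylation in cell-based assays. That is a different drug and a laboratory finding, but it makes dependence on recent exposure plausible.

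Numbers will be small. Section 4.2 aims for at least five patients per drug with a ceiling of 50 enrolled, and Section 1.4 makes biopsy mandatory only at easily accessible sites. A few off-week samples could therefore dominate the regorafenib summary. A mistimed biopsy cannot be corrected at analysis, so the timing has to be settled beforehand.

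**Working it through.** The check is a calendar count.

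Inputs: cycle of 28 days (Section 6); regorafenib on for 21 days and off for 7 (Tables 1 and 2); window of ±7 days (Section 7.1); biopsy after cycle 1 (Section 1.4) or after four weeks (Section 9).

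1. **The plan's own figure.** 21 + 7 = 28 days, which agrees with the stated cycle length. Scheduled regorafenib days are 1–21 and then 29–49; days 22–28 are off.

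2. **Exposure by the nominal time.** Day 28 completes four weeks. A regorafenib patient has by then had 21 scheduled dosing days of 28 (75%); a patient on any other drug has had 28 of 28.

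3. **Time since the last scheduled regorafenib dose (day 21).**
   - Day 28: 28 − 21 = 7 days.
   - Day 29 before the dose: 29 − 21 = 8 days.

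4. **The window.** The text names neither day as the anchor, so both are shown.

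| Nominal day | Window | Regorafenib off-week days | Regorafenib dosing days |
|---|---|---|---|
| 28 | 21–35 (15 days) | 22–28 (7) | 21 and 29–35 (8) |
| 29 | 22–36 (15 days) | 22–28 (7) | 29–36 (8) |

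Under either anchor 7/15 = 47% of permitted days are in the off-week and 8/15 = 53% are dosing days. For the other three drugs all 15 are scheduled dosing days.

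5. **What the dosing days represent.** With anchor 29, all eight are days 1 to 8 of restarted drug (36 − 29 + 1 = 8) after a seven-day gap. With anchor 28, seven are restart days (29–35), and only day 21 belongs to the first uninterrupted run.

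6. **Literal reading.** If after cycle 1 means day 29 or later, the permitted days are 29–36 (anchor 29), all scheduled dosing days. Only a sample taken before the dose on day 29 would still follow the whole break.

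The permitted regorafenib samples thus fall into two exposure states, off-week and recently restarted, and no stated rule separates them.

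**The case against.** A reader might infer that the plan fixes the biopsy in the drug-free week, so that RET and BRAF patients are measured off drug and the exploratory question cannot be answered for them. The documents do not support that, and the case against it is strong.

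- No study day is given. Eight of the 15 window days are regorafenib dosing days under either anchor, and the literal reading can place every sample on restarted drug.
- Off drug here means only that no dose is scheduled. No half-life is given, so exposure after 7 or 8 days cannot be judged. On drug in the other baskets is likewise only by schedule, since interruptions for toxicity are allowed.
- The comparison planned in Section 9 concerns expression. Activation status is listed in Section 1.4 with no planned comparison, and nothing in the documents shows that expression shifts within a week.
- The only exploratory objective (Section 2.3) is mechanisms of resistance. Section 9 addresses it by comparing the progression biopsy with baseline, which this timing does not touch.
- The study calendars and Appendices 6 to 9 were not available. For the regorafenib baskets Section 4.3.1 sends the reader there ("For patients with RET or BRAF fusion to be treated with regorafenib, see Appendix 8, Section 8.1"), and they may give a biopsy day.

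All of this stands, and it limits the point to unspecified timing with an awkward nominal position. It does not remove the point. Sections 1.4, 3.3 and 9 set the time point, and following them as written allows exposure at sampling to differ systematically by basket.

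It is also fair to say that moving the regorafenib sample earlier replaces one imbalance with another, namely duration of treatment. That is a real cost and is counted under the fix.

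**Conclusion.** The point holds in limited form. The plan sets one on-treatment biopsy time without reference to dosing. For the two regorafenib fusion groups, the nominal time is 7 or 8 days after the last scheduled dose, and 7 of the 15 days in the general window are off-week days. Samples from these baskets may mix off-week and just-restarted exposure, which sits poorly with an endpoint defined during treatment and with a comparison between baskets.

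This rests on three assumptions: that the general ±7-day window applies to the biopsy, that the nominal day is 28 or 29, and that the calendars and drug appendices do not set a different day. The direction and size of any effect on expression or activation cannot be stated.

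The share of patients affected cannot be estimated reliably either. The fusion frequencies in Section 1.1 describe melanocytic neoplasms, not this trial's population, and give no figure for MET.

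The consequence is confined to an exploratory measure. Response rate, clinical benefit rate, PFS, OS and safety are unaffected. The change is still worth making because it is cheap and can only be made prospectively.

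**What to change.** - Align Sections 1.4, 3.3 and 9, and the calendars or drug appendices where they mention the biopsy, so that the on-treatment sample is taken on a scheduled dosing day. For capmatinib, ceritinib and entrectinib the existing week-4 time can stay. For regorafenib, place it in the last dosing week of cycle 1 (days 15–21).
- State that the general window does not carry the regorafenib sample past day 21. Otherwise a nominal day 21 with +7 days would reach day 28, the end of the off-week.
- Record the date and time of the last dose with every on-treatment sample, for all drugs, so that unscheduled interruptions are visible too.
- In Section 9, report between-basket changes on all samples, with a sensitivity summary limited to samples taken on drug. Off-week samples stay in the main summary and are identified as such.

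The cost is protocol wording, a case report form entry for the last dose, and possibly a separate visit for the regorafenib biopsy. The regorafenib sample would come about one week earlier than the others (28 − 21 = 7 days if taken on day 21, more if taken earlier in that week). Section 9 should therefore name the different treatment duration as a limitation of the comparison. No dose, dosing schedule or number of biopsies changes.
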